9.3. Statistical analysis

A statistical analyse plan (SAP) will be produced by the statistician and validated by the steering committee before the first statistical analysis. At the end of the dose escalation part of the phase I trial and before opening the expansion cohorts, an IDMC (see section 12.1.2) will be requested to assess safety data and validate MTD based on the statistical report produced by the statistician of the study.

9.3.1. *Patient characteristics at baseline*

The patients entered into the study will be described according to the following characteristics:

- Compliance with eligibility criteria,
- Epidemiological characteristics,
- Clinical and laboratory characteristics,
- Treatment characteristics.

9.3.2. *Endpoint analyses*

9.3.2.1. PHASE I TRIAL (DOSE ESCALATION PART)

- All analyses will be descriptive; no p-values will be calculated.
- Primary endpoint will be analyzed on the population assessable for safety of the phase I trial (escalation part).
- Toxicity observed at each dose level, graded according to the Common Terminology Criteria for Adverse Events v4.0 from the NCI, will be recorded in terms of event type, severity, dates of beginning and end, reversibility and evolution. Data will be gathered in tables summarizing toxicities and side effects for each dose level and cycle.
- DLT will be described in terms of number and incidence rates at each dose level. The number and percentage of patients who will have developed a DLT in each dose level will also be reported.
- Data analyses will be provided by dose groups and for all study patients, combined wherever appropriate.
- Categorical endpoints: best overall response, ORR under treatment and at 6 months, 6-month ORR and 6-month PFR, will be reported in terms of counts by dose level.

- Continuous endpoints will be reported in terms of summary statistics that will include number of patients, median, minimum, and maximum, and additional percentiles if appropriate.
- Survival endpoints (PFS and OS) will be analyzed using the Kaplan-Meier method. The median survival rates will be reported with a 95% confidence interval. Median follow-up will be calculated using the reverse Kaplan-Meier method.
- Missing data will not be imputed.

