8. STUDY ENDPOINTS

8.1. Primary endpoint

Phase I / Dose escalation part

Primary objective of the phase I trial is to establish the recommended phase II dose (RP2D), the maximum tolerated dose (MTD) evaluated on the first cycle (D1 to D21), the safety profile, and the Dose Limiting Toxicities (DLT) of trabectedin given in combination with durvalumab.

Definition:

Dose-limiting toxicity (DLT):

A DLT is defined as an AE or laboratory abnormality that fulfills all the criteria below:

- Begins on the first 21 days of treatment.
- Is considered to be at least possibly related to the study treatment.
- Meets one of the criteria below, graded as outlined or according to NCI-CTCAEv4.03 :
 - Any grade-4 toxicity (except for vomiting without maximal symptomatic/prophylactic treatment and if toxicity is transaminitis, but which have to be resolved at Day 21, i.e. return to Baseline or grade 1).
 - Grade-3 non-haematological toxicity lasting > 7days (except for 1rst episode of nausea without maximal symptomatic/ prophylactic treatment and if toxicity is transaminitis, which have to be resolved at Day 21, i.e. return to Baseline or grade 1).
 - Grade-3 hematologic toxicity lasting for > 7days.
 - Grade 4 neutropenia with fever.
 - Grade > 2 thrombocytopenia with bleeding.

Endpoints:

- Toxicity graded using the common toxicity criteria from the NCI-CTCAE v4.03.
- Incidence rate of DLT at each dose level during the first 21 days.

Phase I / Expansion cohorts

Primary objective of the expansion cohorts is to evaluate preliminary signs of the antitumor activity of trabectedin given in combination with durvalumab in terms of objective response under treatment. Following RECIST v1.1 recommendations ([appendix 3](#)):

- Objective response rate (ORR) is defined as the proportion of patients with complete or partial response (CR, PR) as per RECIST v1.1 criteria.
- Objective response under treatment is recorded from study treatment initiation until the end of treatment and determined once all the data for the patient is known.
- Claimed responses will have to be confirmed at least 4 weeks later to ensure responses identified are not the result of measurement errors.
- **Disease status under treatment, whatever the response observed, will be centrally reviewed for all patients, by an independent expert radiologist. Reviewed data will be used for the efficacy analysis.**

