3.2.3 Primary endpoint

- Dose escalation part

Criteria	eFORM Variables	Control / program (TOL=1)
Toxicity will be graded using the common toxicity criteria from the NCI v4.0.	ADVERSE EVENT FORM AEVENT (adverse event) AESAE (is a serious adverse event) AE_NUMAE (Toxicity number) DT_SAE , DT_AE (date of beginning) DTENDAE (date of the end or death) INIT_INT, MAX_INT (intensity) TRAB_REL (relation to Trabectedin) DURV_REL (relation to Durvalumab) AE_TRA_MOD (Trabectedin modification) AE_DUR_MOD (Durvalumab modification) AE_OUTC (outcome)	Listing of Adverse events + descriptive statistics
Incidence rate of DLT will be reported at each dose level on cycle 1.	CYCLE 1 – TREATMENT DOSE_TRA DOSE-LIMITING TOXICITY FORM DT_EVENT OCC_CYC (occurred for the first 21 days) GR4_TOX GR3_NHT GR3_HT GR3_NEU GR2_THR OTH_DLT	Listing Of DLT + rate of DLT (Number of DLT / TOL) descriptive statistics

- Expansion cohorts

Criteria	eFORM Variables	Control (TOL=1)
Objective response rate, defined as the rate of complete or partial response according to RECIST v1.1	ASSE_CYC (TUMOR ASSESSMENT) DT_MEASC (date of measurement) ME1RTLC-ME5 RTLC (measures of lesions) SUM_RTLC (largest diameters) EVA1RLNMC-EVA5 RLNMC (non-measurable lesions eval) RES_RTLC, RES_RNTLC (target and non-target lesions) OV_REV (overall response) CR=1, PR=2, SD=3, PD=4, NE=5 New variables : NB_BORR (nb of objective response case) END OF STUDY (END_STU) DT_EOS (date of end of study)	Status at each TUMOR ASSESSMENT

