4.3.11 Safety: Adverse events (AE)

Table 11.1. For all patients assessable for efficacy: Number and percentage of AE observed by SOC and type of event

Table 11.2. For each patient assessable for safety: Event number, adverse event, serious adverse event (Y/N), SOC, date of event, initial intensity, maximum intensity, treatment modification, imputability, outcome, date of the end or death

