4.3.12 Safety: Serious adverse events (SAE)

Table 12.1. For all patients assessable for efficacy: Number and percentage of SAE observed by SOC and type of event

Table 12.2. For each patient assessable for safety: Event number, adverse event, SOC, date of event, initial intensity, maximum intensity, treatment modification, imputability, outcome, date of the end or death

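### SAP 3.2.1 promises graded toxicity tables by dose level and cycle, but the SAP's own table list contains none, so the graded-toxicity half of the escalation primary endpoint has no specified summary

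*Protocol*

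**What the plan says.** Protocol 8.1 gives the escalation part two primary endpoints. The first is "Toxicity graded using the common toxicity criteria from the NCI-CTCAE v4.03". The second is the incidence of DLT at each dose level over the first 21 days.

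For the first, Protocol 9.3.2.1 commits to this output: "Data will be gathered in tables summarizing toxicities and side effects for each dose level and cycle". SAP 3.2.1 carries the same sentence, and SAP 3.1 adds that analyses are given by dose group as well as combined.

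SAP 3.2.3, which links endpoints to variables, describes the graded-toxicity output only as "Listing of Adverse events + descriptive statistics". For DLT it specifies incidence at each dose level in cycle 1, calculated as the number of DLTs divided by the patients flagged TOL = 1. SAP 3.2.1 also promises the percentage of patients with a DLT at each level.

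SAP 4.3 then lists the tables. The two summaries of adverse events are:

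- "Table 11.1. For all patients assessable for efficacy: Number and percentage of AE observed by SOC and type of event"
- "Table 12.1. For all patients assessable for efficacy: Number and percentage of SAE observed by SOC and type of event"

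Grade appears in the companion outputs, which go patient by patient: "Table 11.2. For each patient assessable for safety: Event number, adverse event, serious adverse event (Y/N), SOC, date of event, initial intensity, maximum intensity". Table 12.2 does the same for serious events. The report planned for each dose level (SAP 4.1) consists of listings.

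**The concern.** A programmer working from SAP 4.3 would not produce the tables that SAP 3.2.1 promises. The outputs that would be produced either summarise without grade, dose or cycle, or show grade without summarising.

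Two decisions draw on this information. Under Protocol 9.3 the IDMC validates the MTD from the statistician's report. Under Protocol 3.2 and 3.4 the steering committee identifies the RP2D from safety data in both parts of the trial, together with pharmacodynamic data. For either decision, a basic question is how many patients at a dose had a grade 3 or worse event, and when. No listed table answers it.

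**Working it through.** **1. Figures in the plan.** None is in dispute. For context, 3 levels × 6 patients = 18, which matches the stated maximum of patients assessable for safety (Protocol 9.1.1).

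**2. Promise against listed outputs.**

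| | Promised (Protocol 9.3.2.1, SAP 3.2.1) | Tables 11.1, 12.1 | Tables 11.2, 12.2 | Per-dose listings (SAP 4.1) |
|---|---|---|---|---|
| Summarised | yes | yes | no | no |
| CTCAE grade | yes | no | per patient | per patient |
| Dose level | yes | no | no | yes, one report per dose |
| Cycle | yes | no | event date only | event date; cycle 1 and later |
| Population | assessable for safety (TOL) | assessable for efficacy | assessable for safety | patients at that dose |

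No column matches the promise. Efficacy Tables 6 to 10 are at least repeated by treatment arm; the safety tables have no split.

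**3. Population heading.** Efficacy assessability is defined only for the expansion cohorts (Protocol 9.2.2; SAP 2.1.2 and 2.4). SAP 3.2.4 uses TOL for escalation and ELI_EFF for expansion. Taken literally, Tables 11.1 and 12.1 leave out the escalation patients. They also conflict with SAP 3.2.2, which puts the expansion safety analysis on the safety population: a treated patient who is ineligible or not assessable for efficacy belongs in that analysis but not in these tables.

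**4. Unit of counting.** The wording gives a percentage of events. An illustration with assumed counts takes six patients over six cycles and one record per cycle. Two patients have grade 1 nausea every cycle (2 × 6 = 12 records) and four have one grade 3 neutropenia each (4 records).

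- Share of events: nausea 12/16 = 75%, neutropenia 4/16 = 25%, no grade shown.
- Share of patients: nausea 2/6 = 33%, grade 3 neutropenia 4/6 = 67%.

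The ranking reverses.

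**5. DLT rate.** Suppose one patient of six has two DLTs. The SAP 3.2.3 formula gives 2/6 = 33.3%. The percentage of patients, which SAP 3.2.1 also promises, is 1/6 = 16.7%.

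**6. Whether DLT reporting covers the gap.** It does not. The DLT definition (Protocol 3.2) is limited to events starting in the first 21 days. It leaves out grade 3 non-haematological toxicity of 7 days or less, unless another criterion is met, and grade 3 or 4 transaminitis resolved by Day 21. Protocol 1.5 names transaminitis as the potential overlapping toxicity, and Protocol 1.3.3 reports that trabectedin elevations return to grade 1 or less at about day 15. Protocol 6.7.2 notes that immune-mediated events can appear months after the last dose. Such events would show in a graded table by cycle and not in a DLT count.

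**The case against.** The strongest reply is that the SAP keeps the commitment. Section 3.2.1 repeats it, 3.1 requires analysis by dose group, and 4.3 is a list of titles that nowhere claims to be complete. This stands in part: the conflict is inside the SAP, between its text and its table list, and is not a protocol promise that the SAP dropped. It does not supply the missing table, and the outputs that are listed point elsewhere.

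Several stronger readings are tempting, and the documents do not support them.

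- *The whole escalation primary endpoint lacks an incidence output.* DLT incidence and the percentage of patients with a DLT, by dose level, are specified in SAP 3.2.1 and 3.2.3. What they lack is a numbered table and one consistent unit.
- *The event-based DLT rate would misplace the MTD.* The escalation scheme (Protocol 3.3.2) counts patients, so the decision rule is unaffected. The reported rate is what could mislead.
- *Tables 11.1 and 12.1 pool 1, 1.2 and 1.5 mg/m².* Their heading points to the expansion population, where everyone receives the MTD. Pooling would arise only if the heading were widened to all patients without a dose split. With assumed rates of 1/6, 2/6 and 4/6 the table would then show 7/18 = 39%.
- *The percentages are certainly of events.* That is the literal reading, but SAP 3.1 mentions number of patients for categorical endpoints, so patient counts may be intended. Nor is it settled that a persisting event is recorded anew each cycle; Datalisting 3 (SAP 4.1.3) tracks grade changes within an event.
- *The committee cannot see severe toxicity by dose.* The per-dose listings show dose, DLT flag, intensity and imputability. With three to six patients per level, they can be counted by hand.

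**Conclusion.** The point holds in a limited form. SAP 4.3 omits the graded toxicity tables by dose level and cycle that SAP 3.2.1 and Protocol 9.3.2.1 promise. The two summaries it does list lack grade, dose and cycle, leave the counting unit unclear, and name a population that does not cover the escalation part. The DLT rate has no numbered table, and its formula does not match the patient percentage promised beside it.

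The gap concerns the graded-toxicity component of the escalation primary endpoint and the safety summary feeding the RP2D. It does not reach the escalation rule or the MTD definition. Its size cannot be given as a single number because the plan states none; the 75%/25%, 7/18 and 2/6 figures rest on assumed counts and show only how the layouts can differ. It should be corrected before the tables are programmed.

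**What to change.** Amend SAP 4.3, and SAP 3.2.3 for the DLT formula, as follows.

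1. Replace Tables 11.1 and 12.1 with the number and percentage of patients having at least one event, by SOC and term, using each patient's worst CTCAE grade (any grade; grade 3 or higher).
2. Use columns for the dose level assigned at cycle 1 in the escalation part and for cohort in the expansion part.
3. Present cycle 1, each later cycle (or stated groups of later cycles), and all cycles together, so that the promised split by cycle is met.
4. Name the populations: TOL = 1 for the escalation primary analysis, and all treated patients for the RP2D summary. State that this safety population covers both parts, since it is currently defined under the expansion cohorts.
5. Add a numbered DLT table by dose level, counting patients with at least one DLT over TOL patients, and change the SAP 3.2.3 formula to match.

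A further split by relationship to treatment is good practice but optional, as neither document promises it for these tables.

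The cost is SAP wording and programming. Maximum intensity (MAX_INT), relationship to each drug (TRAB_REL, DURV_REL), event dates and cycle 1 trabectedin dose (DOSE_TRA) are already among the SAP 3.2.3 variables.

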9.3.2.2. EXPANSION COHORTS

- All analyses will be descriptive; no p-values will be calculated.
- Analyses will be conducted separately for sarcoma and ovarian cancer patients.
- Primary efficacy endpoint will be analysed based on the eligible and assessable population (see [chapter 10.2](#) for definition):
 - Each patient will be assigned one of the following categories:
 - Complete response
 - Partial response
 - Stable disease
 - Progression
 - Inevaluable for response
 - The rate of objective response (complete or partial response) under treatment will be reported:
 - All eligible and assessable patients ([section 10.2](#)) will be included in the denominator for the calculation of the objective response rate (ORR).
 - The 95% two-sided confidence limits will be provided for the ORR (binomial law).
 - First endpoint conclusions will be based on the objective response rate ORR for all eligible and assessable patients ([section 10.2](#)) after centralized radiological review of the data.
- As regards to the other efficacy endpoints, the analyses will be carried out in the eligible and assessable population:
 - Each patient will be assigned one of the following categories:
 - Complete response
 - Partial response
 - Stable disease
 - Progression
 - Inevaluable for response
 - The rate of best overall response will be calculated as the number of patients alive with the best response (recorded from the start of the treatment) divided by the number of patients eligible and assessable ([section 10.2](#)).
 - The 6-month progression-free rate will be calculated as the number of patients remaining alive and progression-free at 6 months from the start of the treatment divided by the number of patients eligible and assessable ([section 10.2](#)).
 - The 6-month objective response rate will be calculated as the number of patients alive with complete or partial response at 6 months divided by the number of patients eligible and assessable ([section 10.2](#)).
 - The 95% two-sided confidence limits will be provided for the calculated rates (binomial law)
- The safety analysis will be performed on the safety population.
- Quantitative variables will be described using mean and standard deviations if the normality assumption is satisfied, else other descriptive statistics (median, range, quartiles) will be reported.
- Qualitative variables will be described using frequency, percentage and 95% confidence interval (binomial law).
- Survival endpoints will be analysed using the Kaplan-Meier method. The median survival rates will be reported with a 95% confidence interval. Median follow-up will be calculated using the reverse Kaplan-Meier method.

10. ADVERSE EVENTS

10.1. Description of safety evaluation criteria

The safety evaluation will comprise an evaluation of the patient's general condition (ECOG Appendix 1), a physical examination, regular blood tests and the recording of adverse events occurring throughout the study. Toxicity will be evaluated using the NCI-CTCAE v4.03 scale available on the world wide web at <http://ctep.info.nih.gov>. All appropriate treatment areas should have access to a copy of the NCI-CTCAE v4.03.

In an emergency situation, the patient, his/her friends/family or treating physician will contact the investigator to report an event and/or to discuss the treatments to be implemented.

10.2. Definition

10.2.1. *Adverse event*

An adverse event is defined as any untoward medical occurrence which occurs in a patient, a clinical investigation subject. Adverse events include, but are not limited to:

- Abnormal test findings,
- Clinical symptoms and signs,
- Changes in physical examination findings,
- Hypersensitivity,
- Drug abuse,
- Drug dependency,
- Any suspected transmission of an infectious agent via a medicinal product.

As well as signs and symptoms resulting from:

- Drug overdose,
- Drug withdrawal,
- Drug misuse,
- Drug interactions,
- Extravasation,
- Exposure during pregnancy,
- Exposure during breastfeeding,
- Medication error,
- Occupational exposure.

10.2.2. *Serious adverse event*

A Serious Adverse Event (SAE) is defined as an adverse event regardless of the dose and that:

- results in death (fatal) and/or,
- is life-threatening and/or,
- requires inpatient hospitalization or prolongation of existing hospitalization and/or,
- results in persistent or significant disability/incapacity and/or,
- results in congenital anomaly/birth defect and/or,
- is medically significant.

Medical and scientific judgment is exercised in determining whether an event is an important medical event. An important medical event may not be immediately life-threatening and/or result in death or hospitalization. However, if it is determined that the event may jeopardize the patient or may require intervention to prevent one of the other outcomes listed in the definition above, the important medical event should be reported as serious. Examples of such events are intensive treatment in an emergency room or at home for allergic bronchospasm, blood dyscrasias or convulsions that do not result in hospitalization, or development of drug dependency or drug abuse.

Any suspected transmission via a medicinal product of an infectious agent, pathogenic or non-pathogenic, is assessed as a serious adverse event with the seriousness criterion important medical event. The event may be suspected from clinical symptoms or laboratory findings indicating an infection in a patient exposed to a medicinal product. The terms "suspected transmission" and "transmission" are considered synonymous.

Any abnormal laboratory's result resulting as a grade 4 in the CTCAE v4.03 will be considered a serious adverse event even if this event is not clinically relevant.

Whether or not corresponding to the above-mentioned criteria, any other adverse event considered a serious by any IMP, any healthcare professional or any investigator should be handled as a serious adverse event.

10.2.2.1. DEATH

Death as such is the outcome of a SAE or the seriousness criteria and should not be used as the SAE term itself. Instead the cause of death should be recorded as the SAE term. When available, the autopsy report will be provided to the Sponsor.

10.2.2.2. LIFE-THREATENING EVENT

Any event in which the patient was at risk of death at the time of the event; it does not refer to an event which hypothetically might have caused death if it were more severe.

10.2.2.3. HOSPITALIZATION OR PROLONGATION OF HOSPITALIZATION

Any AE requiring hospitalization (or prolongation of hospitalization) that occurs or worsens during the course of a patient's participation in a clinical trial must be reported as a SAE. Prolongation of hospitalization is defined as any extension of an inpatient hospitalization beyond the stay anticipated/required for the initial admission, as determined by the Investigator or treating physician.

Hospitalizations that do not meet criteria for SAE reporting are:

- Reasons described in protocol [e.g., investigational medicinal product (IMP) administration, protocol-required intervention/investigations, etc]. However, events requiring hospitalizations or prolongation of hospitalization as a result of a complication of therapy administration or clinical trial procedures will be reported as SAEs.
- Hospitalization or prolonged hospitalization for technical, practical or social reasons, in absence of an AE. However, these circumstances will be collected in the CRF.
- Pre-planned hospitalizations: Any pre-planned surgery or procedure must be documented in the source documentation and collected in the CRF. Only if the pre-planned surgery needs to be performed earlier due to a worsening of the condition, should this event (worsened condition) be reported as a SAE.

10.2.3. *Non serious adverse event*

A non-serious adverse event is an adverse event whose characteristics do not meet the criteria of a serious adverse event.

10.2.4. *Adverse effect*

An adverse effect is any untoward and unintended responses to an experimental drug regardless of the dose.

10.2.5. *Expected/Unexpected character*

An unexpected adverse event is an event whose nature, severity/intensity/frequency or outcome does not correspond to the information shown within the reference document for the study. The Sponsor will use as the reference safety information for the evaluation of listedness/expectedness the most updated Investigator's Brochure (IB) and/or Summary Product Characteristic (SmPC) for the studied IMP.

In practice, the term "new effect" is sometimes used as a synonymous of "unexpected adverse effect".

10.2.6. *Intensity criterion*

The CTEP Active Version of the NCI Common Terminology Criteria for Adverse Event (CTCAE) will be utilized for AE reporting.

The intensity of adverse events not listed in this classification will be assessed using the following descriptors:

Mild (grade 1): does not affect the patient's usual daily activities,

Moderate (grade 2): disturbs the patient's usual daily activities,

Severe (grade 3): prevents the patient's usual daily activities,

Very severe (grade 4): requires critical care/life-threatening,

Death (grade 5).

10.2.7. *New information*

A new information is any new safety data that could lead to reevaluate the ratio between the benefits and risks of the research or the investigational product, to modify the use of the investigational product, the conduct of the research or the research documents or to suspend or interrupt or modify the protocol of research or similar research.

For trials of first administration or use of a health product in persons without any conditions: any serious adverse reactions. The study TRAMUNE is not concerned by this situation.

10.2.8. *Special considerations*

Certain product safety monitoring reports should be forwarded even if there is no associated adverse event. These reports involve circumstances that may increase the patient/consumer's risk of developing adverse events.

These circumstances include:

- medication errors,
- exposure during pregnancy,
- exposure during breastfeeding,
- overdose,
- misuse,
- extravasation,
- occupational exposure.

Some of these special circumstances are considered in more details below.

Medications errors: a medication error is any preventable event that may cause or lead to inappropriate medication use or patient harm while the medication is in the control of the healthcare professional, patient, or consumer. Such events may be related to professional practice, healthcare products, procedures, and systems, including: prescribing; order communication; product labeling, packaging, and nomenclature; compounding; dispensing; distribution; administration; education; monitoring; and use.

A medication error does not necessarily involve the administration of the product (e.g. the error may have been corrected prior to administration of the product).

Potential medication errors or "near-misses," which are individual reports of information or complaints about product name, labeling, or packaging similarities that do not involve a patient, are also reportable.

* Exposure during pregnancy: exposure during pregnancy refers to pregnancies where the fetus (from pre-embryo to birth) may have been exposed at a given time during pregnancy to a medicinal product (or a blinded treatment). Even if there is no associated adverse event, exposure during pregnancy must always be reported. It can indeed provide the opportunity to obtain pregnancy outcome important information where appropriate.

Exposure during pregnancy may occur either:

- Through maternal exposure
 - * A female becomes, or is found to be, pregnant either:
 - While receiving a medicinal product
 - After discontinuing a medicinal product
 - During or following environmental exposure to a medicinal product (eg, a nurse reports she is pregnant and that she was exposed to chemotherapy drugs via inhalation or after accidentally overturning a bottle)

or

- Through paternal exposure

- * A male has been exposed to a medicinal product (either due to treatment or environmental circumstances) prior to or around the time of conception and/or is exposed during the partner pregnancy.

* Exposure during breastfeeding: exposure during breastfeeding occurs where an infant or child may have been exposed through breast milk to a medicinal product during breastfeeding by a female taking the product.

All drug exposure during breastfeeding cases are reported, whether or not there is an associated adverse event.

